3. STUDY POPULATION

3.1. List the number of subjects to be enrolled.

50 patients - 25 study subjects in Group A - Intervention arm, 25 study subjects in Group B
- Control arm

3.2. Criteria for Recruitment

All patients admitted to SICU (ward 21 and ward 23) will be screened for inclusion and exclusion criteria. Patients will then be recruited if the criteria are fulfilled.

3.3. Inclusion Criteria

- 1) At least 60 years old
- 2) Mechanically ventilated within 3 days of ICU admission
- 3) expected to be mechanically ventilated for more than 3 days at time of recruitment
- 4) Able to ambulate with or without a gait aid before hospitalization
- 5) Able to be enterally fed within 48 hours of ICU admission

3.4. Exclusion Criteria

- 1) Unable to follow commands at baseline before hospital admission (e.g. Severe dementia)
- 2) Acute condition where cycling is a contraindication (e.g. leg fracture)
- 3) not expected to survive the subsequent 48 hours
- 4) Body habitus unable to fit the cycle ergometry
- 5) Patients at high risk of refeeding (i.e. NUTRIC score ≥ 5): malnourished patients with anorexia nervosa, chronic malabsorption syndromes, chronic alcoholism, or patients with massive weight loss.
- 6) Extremes of BMI: i.e. BMI < 16 or > 30
- 7) Liver failure
- 8) Cycling exemptions precluding cycling within the first 4 days of mechanical ventilation
- 9) Requirement for inspired oxygen content (FiO₂) greater than 0.8
- 10) Expected to be on renal replacement therapy for longer than 12 hours per session
- 11) PEEP > 15 mmHg
- 12) Air leaks through chest drains
- 13) Palliative goals of care or limitation of treatment established by the CARE form
- 14) Readmissions to ICU

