3.4.1 Temporary cycling exemptions (to be reviewed before daily cycle ergometry sessions)

1. Respiratory
 - a. Persistent O₂ saturation <88%
2. Cardiovascular
 - a. Active myocardial ischemia (MI)
 - b. Unstable or uncontrolled arrhythmia
 - c. Any increase in vasoactive infusions within the last 2 hours
 - d. Mean arterial pressure (MAP) <60 or >110 mmHg within the last 2 hours
 - e. Heart rate (HR) <40 or >140 beats per minute (BPM) within the last 2 hours
3. Receipt of neuromuscular blocking agents within the last 4 hours
4. Uncontrolled pain
5. Severe agitation (Richmond Agitation and Sedation Scale, RASS [48]) >2) within the last 2 hours
6. Change in goals to palliative care
7. Team perception that cycling was not appropriate, despite absence of above exemption criteria

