6.2. Study Visits and Procedures

a. Screening and Procedures

Patients admitted to SICU NUH will be screened based on inclusion and exclusion criteria within 24 hours of admission. If the patient is sedated, the PIF leaflet will be given to the listed next of kin or the study subject if there are not cognitively impaired. The patient or NOK will be given 24 hours to consider the PIF and to ask any questions before recruitment. Once recruited, randomisation will occur and the patient will be allocated into each treatment arm.

b. Study Visits and Procedures

After recruitment, the patients allocated to group A will undergo baseline quadriceps muscle ultrasound and daily indirect calorimetry measurements while intubated. The measured REE and energy expenditure from CE will be recorded on the patient's notes. The dose of enteral feed will then be prescribed and administered to the patient. If the patient gets extubated during the study period of 14 days, the patient will be fed based on the last

recorded REE measured by the IC with the addition of estimated energy expenditure from the cycle ergometry.

The study subjects will undergo quadriceps ultrasound measurements up to 4x during the study period (twice a week for 14 days). CE will commence daily for 60mins for up to 14 days if there are no temporary cycling exemptions (see 3.4.1) and can be terminated by 3.4.2.

c. Final Study Visit:

Bedside functional outcome measurements will be obtained at ICU discharge and at day 14 of the study.

d. Post Study Follow up.

Bedside functional outcome measurements will be performed on patients at hospital discharge.

e. Discontinuation Visit and Procedures

Subjects may withdraw voluntarily from participation in the study at any time. Subjects may also withdraw voluntarily from receiving the study intervention for any reason. If voluntary withdrawal occurs, the subject will be asked to continue scheduled evaluations, complete an end of study evaluation, and be given appropriate care.

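### Do exclusion 8 and inclusion 2 of the protocol clash with the screening and randomisation timetable?

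*Protocol*

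**What the plan says.** Section 3.4, item 8, excludes patients with "Cycling exemptions precluding cycling within the first 4 days of mechanical ventilation". Section 3.2 applies the criteria to all admissions to the surgical ICU and recruits those who meet them.

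Section 6.2a sets the timetable. Patients "will be screened based on inclusion and exclusion criteria within 24 hours of admission"; the patient or next of kin then has 24 hours to consider the leaflet (Section 10.1 allows up to 24 hours). After that, "Once recruited, randomisation will occur and the patient will be allocated into each treatment arm".

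Inclusion 2 in Section 3.3 reads "Mechanically ventilated within 3 days of ICU admission".

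The only cycling exemptions listed are in Section 3.4.1. They are described as temporary and are reviewed ahead of each daily session. Several look back only a few hours, for example "Any increase in vasoactive infusions within the last 2 hours" and "Receipt of neuromuscular blocking agents within the last 4 hours". Section 6.2b then has daily cycling go ahead "if there are no temporary cycling exemptions".

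**The concern.** Two things look out of step.

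First, exclusion 8 covers four days of ventilation but is applied at entry, when much of that time has not yet happened. If it is read together with Section 3.4.1, a screener might exclude a patient for any exemption present at the screen, or only for one foreseen to rule out cycling through day 4. A patient with a recent rise in a vasoactive infusion would be out under the first reading and in under the second. After allocation, the same event would only hold up that day's session.

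Second, a patient first ventilated on day 2 or 3 satisfies inclusion 2 but would not yet be ventilated at a screen done in the first 24 hours.

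At stake is whether two screeners following the text would enrol the same patients, and therefore to whom the result applies. A more serious worry would be exclusion 8 working as a removal after randomisation, which would undercut the intention-to-treat analysis.

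**Working it through.** The protocol states no figure to reproduce here. The check is a timeline in hours from ICU admission, followed by a comparison of the sections.

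**Inputs**

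- Screening time S: 0 to 24 (Section 6.2a).
- Consent time C: 24 (Section 6.2a), or 0 to 24 (Section 10.1).
- Start of ventilation V: at most 72 (inclusion 2). Assumed to be at or after admission.
- Length of the exclusion 8 window: 4 × 24 = 96, counted from V.

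**Randomisation time.** R = S + C, assuming the leaflet is handed over at the screen.

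- Section 6.2a: from 0 + 24 = 24 to 24 + 24 = 48.
- Section 10.1: from 0 + 0 = 0 to 24 + 24 = 48.

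**Part of the exclusion 8 window still ahead at randomisation.** Hours ahead = V + 96 − R.

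| V | Window ends | Ahead if R = 48 | Ahead if R = 24 |
|---|---|---|---|
| 0 | 96 | 48 (48/96 = 50%) | 72 (72/96 = 75%) |
| 24 | 120 | 72 (72/96 = 75%) | 96 (96/96 = 100%) |

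Earlier randomisation under Section 10.1 only increases the hours ahead. At least half of the window is therefore unobserved at entry under the stated assumptions, and item 8 has to be a forecast.

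**Inclusion 2 against the screening limit.**

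- After the 24-hour screen: (72 − 24)/72 = 48/72, two thirds of the window.
- After 48 hours: (72 − 48)/72 = 24/72, one third.

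These are shares of time, not of patients; the protocol gives no distribution of ventilation start times.

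**Reading exclusion 8 with the rest of the protocol**

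- Item 8 does not cite Section 3.4.1. The link is inferred because that is the only list of cycling exemptions, and its heading gives it another purpose, the check before each session.
- Item 8 concerns exemptions that rule out cycling over the four-day period. An event in the last 2 or 4 hours, re-checked daily, does not by itself do that. The wording therefore favours the prospective reading.
- Forecasts at entry are used elsewhere: inclusion 3, exclusion 3 and exclusion 10 all rest on what is expected. Item 8 lacks that word but is the same kind of judgement.

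**Reading the screening rule.** Section 6.2a says when screening takes place. It does not say that screening is done once or that a patient not yet ventilated is closed to later consideration. A first look within 24 hours, with follow-up to day 3, is compatible with both sections.

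**Effect on the comparison**

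- Sections 3.2 and 6.2a put eligibility before recruitment, and recruitment before randomisation. A judgement made before allocation is known cannot differ by arm, except by chance.
- Section 3.5 gives two grounds for withdrawal: refusal or withdrawal of consent, and review by the ethics board. Exclusion 8 is neither.
- Section 3.6 says drop-outs are not replaced and are evaluated by intention to treat.
- Exemptions and stopped sessions after allocation are dealt with in Sections 3.4.1 and 3.4.2, which affect sessions and not membership of the trial.

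On the text as written, exclusion 8 does not act after randomisation.

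**The case for a change.** The best case for an amendment is that eligibility ought to be reproducible. The protocol marks its other forecasts with *expected*, so a careful reader may take the missing word in item 8 as deliberate. Changes in vasoactive support, blood pressure excursions and neuromuscular blockade are plausible early in ventilated surgical patients, so the two readings could diverge on real candidates. In a pilot of 50 patients a clear account of who was eligible matters, these rules belong in the protocol and not in a statistical analysis plan, and a few words would settle it.

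Much of this stands. The word is missing, repeat screening is not mentioned, and clearer wording would be cheap. What does not stand is that the two readings are equally open: excluding for any momentary exemption gives little weight to the four-day qualifier. Nor is inclusion 2 contradicted, since silence about repeat screening does not forbid it. Forecast criteria always leave screeners some room, and that room is used before allocation.

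**Conclusion.** No change follows. The quotations and the arithmetic hold: 50% to 100% of the exclusion 8 window lies ahead at randomisation for ventilation starting 0 to 24 hours after admission and randomisation at 24 to 48 hours, and two thirds of the inclusion 2 window falls after the 24-hour screen. These figures show that exclusion 8 looks forward and that screening may need to be repeated. They do not show an error in the design.

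The gap is one the site can fill sensibly, by judging exclusion 8 prospectively before allocation and looking again at patients ventilated later within the three days. The residual effect is on who is enrolled and how the population is described, with no consequence shown for bias, effect size or power.

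The conclusion rests on three points: eligibility is settled before allocation is known, as Sections 3.2 and 6.2a imply; no randomised patient is removed under exclusion 8, as Sections 3.5 and 3.6 imply; and the randomisation times are derived from the screening and consent periods, since the protocol gives no hour. If exclusion 8 were in practice used to drop patients after randomisation, the answer would be different, but nothing in the protocol provides for that.

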3.4.1 Temporary cycling exemptions (to be reviewed before daily cycle ergometry sessions)

1. Respiratory
 - a. Persistent O₂ saturation <88%
2. Cardiovascular
 - a. Active myocardial ischemia (MI)
 - b. Unstable or uncontrolled arrhythmia
 - c. Any increase in vasoactive infusions within the last 2 hours
 - d. Mean arterial pressure (MAP) <60 or >110 mmHg within the last 2 hours
 - e. Heart rate (HR) <40 or >140 beats per minute (BPM) within the last 2 hours
3. Receipt of neuromuscular blocking agents within the last 4 hours
4. Uncontrolled pain
5. Severe agitation (Richmond Agitation and Sedation Scale, RASS [48]) >2) within the last 2 hours
6. Change in goals to palliative care
7. Team perception that cycling was not appropriate, despite absence of above exemption criteria

3.4.2 Indication for the premature termination of cycle ergometry

1. unplanned extubation
2. suspected new unstable or uncontrolled arrhythmia, or suspected myocardial ischaemia
3. ICU physician request to terminate session
4. PT terminated session due to physiologic concerns.
5. Study subject request to terminate session.

3.5. Withdrawal Criteria

- 1) Patient subsequent refusal or withdrawal of consent
- 2) Upon DSRB review

3.6. Subject Replacement

Subjects who drop out will not be replaced and will be evaluated based on intention to treat

4. STUDY SCHEDULE

Patients recruited and randomised to Group A (intervention), will undergo daily indirect calorimetry to obtain their resting energy expenditure (REE), have their enteral feeds titrated to the REE, and commenced on the cycle ergometry for up to 14 days. In Group B

(control), patients will have standard care and nutrition prescribed by the treating physician and standard physiotherapy as determined by the treating physician.

5. STUDY DESIGN

5.1. Summary of Study Design

This is a single centre randomised single blinded controlled study examining the effects of targeted feeding based on indirect calorimetry and early exercise based on the cycle ergometry.

6. METHODS AND ASSESSMENTS

6.1. Randomisation and Blinding

Randomisation will be done by simple randomisation service via sealedenvelope.com. Group A will be the intervention group; Group B will be the control group. Unmasking can occur at the request of the treating physician or upon approval from the principal investigator. The study participant will not be blinded as it will be not be possible to blind the use of the cycle ergometry machine to the study participant. Assessors of the outcome measures e.g. muscle ultrasound operator and functional outcomes will be blinded to the interventions.

6.2. Study Visits and Procedures

a. Screening and Procedures

Patients admitted to SICU NUH will be screened based on inclusion and exclusion criteria within 24 hours of admission. If the patient is sedated, the PIF leaflet will be given to the listed next of kin or the study subject if there are not cognitively impaired. The patient or NOK will be given 24 hours to consider the PIF and to ask any questions before recruitment. Once recruited, randomisation will occur and the patient will be allocated into each treatment arm.

b. Study Visits and Procedures

After recruitment, the patients allocated to group A will undergo baseline quadriceps muscle ultrasound and daily indirect calorimetry measurements while intubated. The measured REE and energy expenditure from CE will be recorded on the patient's notes. The dose of enteral feed will then be prescribed and administered to the patient. If the patient gets extubated during the study period of 14 days, the patient will be fed based on the last

recorded REE measured by the IC with the addition of estimated energy expenditure from the cycle ergometry.

The study subjects will undergo quadriceps ultrasound measurements up to 4x during the study period (twice a week for 14 days). CE will commence daily for 60mins for up to 14 days if there are no temporary cycling exemptions (see 3.4.1) and can be terminated by 3.4.2.

c. Final Study Visit:

Bedside functional outcome measurements will be obtained at ICU discharge and at day 14 of the study.

d. Post Study Follow up.

Bedside functional outcome measurements will be performed on patients at hospital discharge.

e. Discontinuation Visit and Procedures

Subjects may withdraw voluntarily from participation in the study at any time. Subjects may also withdraw voluntarily from receiving the study intervention for any reason. If voluntary withdrawal occurs, the subject will be asked to continue scheduled evaluations, complete an end of study evaluation, and be given appropriate care.

7. SAFETY MEASUREMENTS

7.1. Collecting, Recording and Reporting of “Unanticipated Problems Involving Risk to Subjects or Others” – UPIRTSO events to the NHG Domain Specific Review Boards (DSRB)

UPIRTSO events refers to problems, in general, to include any incident, experience, or outcome (including adverse events) that meets ALL of the following criteria:

1. Unexpected

In terms of nature, severity or frequency of the problem as described in the study documentation (eg: Protocol, Consent documents etc).

2. Related or possibly related to participation in the research

Possibly related means there is a reasonable possibility that the problem may have been caused by the procedures involved in the research; and

3. Risk of harm

Suggests that the research places participants or others at a greater risk of harm (including physical, psychological, economic, or social harm) than was previously known or recognized.

Reporting Timeline for UPIRTSO Events to the NHG DSRB.

1. Urgent Reporting: All problems involving local deaths, whether related or not, should be reported immediately – within 24 hours after first knowledge by the investigator.
2. Expedited Reporting: All other problems must be reported as soon as possible but not later than 7 calendar days after first knowledge by the NHG investigator.

7.2. Collecting, Recording and Reporting of Serious Adverse Events (SAEs)

1. For Principal Investigator initiated Trials

Previous studies have showed the safety of the cycle ergometry. All ICU and High dependency patients are closely monitored. In the event of any adverse cardiovascular or respiratory events, the cycling can be terminated and the study subject allowed to rest. All SAEs that are unexpected and related to the cycling will be reported. The PI will be responsible for informing DSRB no later than 15 calendar days after first knowledge that the case qualifies for expedited reporting. Follow-information will be actively sought and submitted as it becomes available.

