2.3. Secondary Objectives

The secondary outcomes are 1) ICU mortality 2) ICU and hospital length of stay 3) functional assessments of mobility such as Chelsea Critical Care Physical Assessment Tool (CPAx) and Functional Status Score for the ICU (FSS-ICU). 4) Assessment of strength i.e Handgrip Strength using dynamometer and Medical Research Council Sum Score (MRC-SS).

2.4. Potential Risks and benefits:

a. End Points - Efficacy

We would expect patients who undergo early exercise and feeding have improved functional outcomes, mobilise earlier and avoid problems of prolonged hospital stay. This would avoid the severe problems of deconditioning and muscle loss in the older patient.

b. End Points - Safety

Patients might have some mild cardiovascular instability as with any exercise regimen and hence the strict temporary exclusion criteria before the commencement of the exercise. Patients are closely monitored on ICU and any deviation from baseline parameters will lead to the termination of the exercise cycle ergometry. Other ICU studies have showed the

safety of the cycle ergometry in this group of ICU patients.

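### The SAE reporting rule in section 7.2 names cycling only, leaving a narrow class of serious events from study-directed feeding with no clear duty to report

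*Protocol*

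**What the plan says.** Section 7.2 of the protocol gives the rule specific to serious adverse events in this investigator-initiated trial: "All SAEs that are unexpected and related to the cycling will be reported". The rest of that section also deals with the safety of cycling and with stopping a cycling session. It does not mention feeding.

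The intervention is wider than that. Section 5.1 says the trial examines the effects of "targeted feeding based on indirect calorimetry and early exercise based on the cycle ergometry". Under section 4, Group A patients are to "have their enteral feeds titrated to the REE, and commenced on the cycle ergometry for up to 14 days". Under section 6.2 b, a patient extubated within the 14 days is fed according to the last "recorded REE measured by the IC with the addition of estimated energy expenditure from the cycle ergometry". In Group B, by contrast, the treating physician prescribes nutrition.

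Section 7.1 sets a separate and more general rule for unanticipated problems (UPIRTSO events). An event must be unexpected against the study documentation, be related or possibly related to the research, and meet a third criterion: "Suggests that the research places participants or others at a greater risk of harm" than was already known or recognised. All three must hold. Under the section's reporting timeline, problems involving local deaths are reported within 24 hours whether related or not, and all other problems within 7 calendar days.

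**The concern.** The trial tests feeding and cycling as one package, and the protocol sets both in Group A. One would expect a serious event caused by either component to meet the same reporting threshold. Section 7.2 instead ties reporting to cycling alone. An event due to study feeding has to qualify under 7.1, which adds a condition that 7.2 does not impose.

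At stake is what the review board learns about a combination that section 9.1 describes as not previously studied. For some events the board would have to be told if cycling was the cause, but not if study feeding was. Reporting scope is fixed in the protocol itself, so this is a stated rule drawn too narrowly, not a detail left to a later document.

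**Working it through.** No arithmetic applies. The check is to take SAEs that are alike except for their cause and apply both sections to each.

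**Inputs**

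- Components of the intervention (sections 4, 5.1 and 6.2 b): two, calorimetry-directed feeding and cycling.
- Conditions in 7.2: serious, unexpected, and related to cycling.
- Conditions in 7.1: unexpected, related or possibly related to the research, and suggesting greater risk than known. All three are required. Deaths are reportable regardless of relatedness.
- Planned exposure to study feeding (section 3.1): "25 study subjects in Group A - Intervention arm", that is 25 of 50 patients.

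**Applying the rules to an unexpected SAE**

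| Case | Cause | Fatal? | 7.1 criterion 3 met? | Under 7.1 | Under 7.2 | Must be reported? |
|---|---|---|---|---|---|---|
| a | Cycling | No | No | No | Yes | Yes |
| b | Study feeding | No | No | No | No | No |
| c | Study feeding | No | Yes | Yes, 7 days | No | Yes |
| d | Study feeding | Yes | Either | Yes, 24 hours | No | Yes |

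Cases c and d show that 7.1 already covers feeding when all its criteria are met or the patient dies. The asymmetry lies between a and b, which differ only in cause.

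**Can case b occur?** It needs an event that meets criterion 1 but not criterion 3. The two use different yardsticks. Criterion 1 compares the event with what the study documentation describes. Criterion 3 compares it with what was previously known or recognised, and is not limited to study documents. An SAE could therefore be absent from the trial's documents, and so unexpected, yet be judged a recognised risk of enteral feeding. The wording leaves room for case b, but gives no means of saying how often it would arise.

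**The case against.** The strongest answer is that 7.1 does nearly all the work. Its relatedness criterion takes in every research procedure, and calorimetry-directed feeding is one. For events that qualify, it is stricter than 7.2: a possible relation suffices and the limit is 7 days, not 15. A serious, research-related event that is worse or more frequent than described will usually be evidence of greater risk than recognised, so criteria 1 and 3 largely overlap. This stands, and it is why the gap is narrow.

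A second answer is that the 7.1 timeline is not strictly confined to events meeting all three criteria. Its limb on deaths sets relatedness aside, so its reference to all other problems might be read broadly too. That reading is possible. But the phrase stands under the timeline for UPIRTSO events, and the departure is spelled out for deaths only. The better reading keeps the three criteria for the rest. At the least, the protocol leaves the matter to interpretation.

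Three stronger readings are tempting and should not be drawn:

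- *That feeding-related SAEs go unreported in this trial.* This is true of 7.2 read alone, but not of the protocol, as cases c and d show.
- *That the exclusion in section 3.4 of "Patients at high risk of refeeding" illustrates the gap.* It is weak support. Because high-risk patients are excluded, a serious refeeding event in an enrolled patient would tend to suggest more risk than the protocol assumed, and so to meet criterion 3.
- *That the 7-day limit in 7.1 and the 15-day limit in 7.2 contradict each other.* Both are maxima for informing the same board, and meeting the shorter satisfies both.

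Nor does the exercise-only safety text in section 2.4 b ("Patients might have some mild cardiovascular instability as with any exercise regimen") add much. It describes expected effects and is not a reporting rule.

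**Conclusion.** The point holds in a limited form. Section 7.2 sets an SAE rule for one of the two components, and 7.1 makes up most but not all of the difference. The residual class is a non-fatal, unexpected, feeding-related SAE judged not to meet criterion 3 of 7.1.

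The conclusion rests on two assumptions. The first is the narrower reading of the 7.1 timeline. The second is that criteria 1 and 3 can come apart, which depends partly on which feeding risks the consent documents list; those documents are not available here.

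The size cannot be given as a number, because the protocol states no event rate. The 25 Group A patients are the planned exposure, not a count of events or of patients affected. The point does not touch the endpoint, the randomisation or the analysis. It is a small inconsistency in safety reporting, worth correcting because correction is cheap.

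**What to change.** In section 7.2, extend the relatedness condition so that it reads: *related to the cycling or to the study-directed (calorimetry-based) feeding*. Leave the rest of the sentence and its causality standard as they are. Widening the test to events possibly related to any study procedure would go beyond the defect, since nothing here shows the causality standard in 7.2 to be at fault.

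The cost is one phrase in the protocol and possibly some additional SAE reports, in a number the protocol gives no basis for estimating. No procedure or visit is added, and no feeding or cycling rule changes.
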